4.3.15 Total score of subjective ocular symptoms upon instillation

The total score of subjective ocular symptoms upon instillation (ranging from 0 to 18) will be calculated by adding the individual scores of the 6 following symptoms: irritation/burning, stinging, itching, tearing, eye dryness feeling, foreign body sensation. If any individual score is missing, the total score will also be missing.

4.3.16 Far best corrected visual acuity

Far best corrected visual acuity will be calculated in Log Mar as: $\text{Log}_{10} (10 / \text{Visual acuity})$ with Visual acuity expressed in /10 unit.

4.3.17 AE time to occurrence

Time to occurrence (days) of an AE will be calculated as follows: Date of onset – Date of IMP first instillation.

4.3.18 AE duration

Duration (days) of an AE will be calculated as follows: (Date of recovery – Date of onset) + 1.

5 DESCRIPTION OF THE STUDY POPULATION

5.1 Disposition of patients

The number of enrolled patients will be presented overall. The number (%) of patients included in Azopt® Safety set will be presented overall. The number (%) of patients included in each other analysis set (Safety, ITT, m-ITT and PP) will be presented by treatment group and overall. It will also be presented by possible impact of COVID-19 pandemic classes.

The number (%) of patients by country will be presented by treatment group and overall, for each analysis set. The number (%) of patients by country will be also presented for patients who prematurely discontinued the study for COVID-19 crisis and by possible impact of COVID-19 pandemic classes for the Safety set.

The number (%) of patients per visit as considered in the analysis will be described by treatment group and overall for the Safety set, for the ITT set (if it differs from the Safety set) for the m-ITT set and for PP. It will also be described by possible impact of COVID-19 pandemic classes for each population.

A listing of patients with populations, treatment group (planned group and actual group), worse eye of the enrolled patients and possible impact of COVID-19 pandemic classes and a listing of visits and visits as considered in the analysis (see Sections 4.1 and 4.2) will be produced for the Safety set.

The number (%) of patients who prematurely discontinued the study and the primary reason for discontinuation will be presented by treatment group and overall for the Safety set, ITT set (if it differs from the Safety set) and m-ITT set. A listing will be produced presenting the patients who prematurely discontinued the study with the detailed reason for discontinuation. The number (%) of patients by country will be also presented for patients who prematurely discontinued the study and for those who prematurely discontinued for COVID-19 crisis.

The number (%) of patients with at least one major deviation, the number (%) of patients with only minor deviations (without major deviations) and the number (%) of patients with minor deviations (including those with major deviations) will be presented by treatment group and overall for the m-ITT set. The reasons for deviation will also be described for the m-ITT set and an individual patient data listing with all minor/major deviations will be provided. This description will also be performed possible impact of COVID-19 pandemic classes.

A listing of patients excluded from the Azopt® Safety, Safety, ITT, m-ITT and PP sets, presenting the reason for exclusion, will be produced on the enrolled patients' population.

5.2 Demographic and baseline characteristics

The demographic and baseline characteristics of the patients will be described overall and by treatment group for the m-ITT set, Safety set, ITT set (if it differs from the Safety set) and PP set.

The following characteristics will be summarised:

- Demographic characteristics:
 - Age (years) as continuous and in classes (<65, ≥65 years old)
 - Gender
 - Gender by age class (<65, ≥65 years old)
- Medical history (*)
 - Ocular medical history other than the studied disease
 - Systemic medical history
- Surgical history (*)
 - Ocular surgical history related to another disease than the studied one
 - Systemic surgical history

(*) Diagnoses (for medical history) and surgical procedures (for surgical history) will be coded using the Medicinal Dictionary for Regulatory Activities (MedDRA) version the most recent possible at the database lock. Number (%) of patients will be presented by SOC and PT by treatment group and overall.

- Ocular treatments (**)
 - Previous ocular treatments
 - Concomitant ocular treatments
- Non-ocular treatments (**)
 - Previous non-ocular treatments
 - Concomitant non-ocular treatments

(**) All previous and concomitant ocular and non-ocular treatments will be coded using the World Health Organisation-Drug Dictionary (WHO-DD version Q1 2018). Treatments will be summarised according to the Anatomical therapeutic chemical (ATC) class (level 2 and level 4) of the WHO-DD dictionary by treatment group and overall. A previous treatment will be defined as a treatment stopped prior to (or the same day as) the first instillation of T4032 or Lumigan®. A concomitant treatment will be defined as a treatment i) started after (or the same day as) the first instillation of the T4032/ Lumigan®, ii) started prior to and continued after the first instillation of the T4032/ Lumigan®. If the classification is not possible due to partial start/end date(s) of treatment, the treatment will be considered as concomitant.

- History of glaucoma or ocular hypertension:
 - Diagnosis in the worse and contralateral eye (Ocular hypertension / Primary Open Angle Glaucoma / Secondary Open Angle Glaucoma: Exfoliation Glaucoma / Secondary Open Angle Glaucoma: Pigmentary Glaucoma)
 - Time from diagnosis in the worse and contralateral eye (months)
 - Previous treatment (Bimatoprost/Latanoprost/Tafluprost/Travoprost/Other)
 - Surgical history related to the glaucoma or ocular hypertension in the worse and contralateral eye (by SOC and PT)
- Results of the automated visual field (Normal/Abnormal; If abnormal, clinically significant [Yes/No]) for the worse and the contralateral eyes
- Central corneal thickness measurement (μm) for the worse and contralateral eye as continuous and in classes (<555 , $\geq 555 \mu\text{m}$)
- Fundus examination (listing)
- IOP data during run-in period: Descriptive statistics will be performed on IOP at 08:00, for the worse and contralateral eye, at each assessment time (i.e., screened visit and randomisation visit). Change from screening to randomisation will be described. The descriptions will also be performed depending on the wash-out duration (≤ 8 days, >8 days).

Data regarding contraception status and pregnancy test results (for women) will be presented in an individual data listing (Section 16.2).

In addition, the following data will be described for the Safety set:

- Number of patients and cumulative time of exposure (in days)
- Number of patients and cumulative time of exposure (in days) by age group (<65 years old, ≥ 65 and <75 years old, ≥ 75 and <85 years old, ≥ 85 years old) and gender
- Number of patients and cumulative time of exposure (in days) by IMP exposure in classes (<1 month, ≥ 1 and <3 months, ≥ 3 months)

Demographics characteristics, history of glaucoma or ocular hypertension, automated visual field, central corneal thickness measurement, IOP data during run-in period, baseline values of IOP will be also presented for patients who prematurely discontinued the study for COVID-19 crisis for the Safety set, by possible impact of COVID-19 pandemic classes for m-ITT, Safety and PP sets and according to the following groups: Patients from ITT set included in m-ITT set versus Patients from ITT set not included in m-ITT set.

Baseline values of the efficacy and safety endpoints will be provided in statistical tables with assessments at Week 6 (if applicable) and Week 12 (see Sections 6 and 7).

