All the ocular assessments have to be performed in both eyes.

- (1) Ocular symptoms (irritation/burning, stinging, itching, tearing, eye dryness feeling, foreign body sensation), scored using 0-3 scale, will be collected by the investigator /delegate.
- (2) At Screening Visit, one IOP measurement should be performed at 08:00 (\pm 30 minutes). At Day 1, Day 42/Week 6 and Day 84/Week 12, IOP should be measured at three time points: 08:00, 10:00 and 16:00 (each \pm 30 minutes) with a.m. measurements of IOP at least 2 hours apart. IOP measurements should be done at the same hours (\pm 30 min) than Day 1, by the same investigator and using the same technique (Goldmann applanation tonometer) for all visits.
- (3) To be performed if fundus examination / central corneal thickness measurement / automated visual field not done within the previous 12 months and/or results dating from the last 12 months not available.
- (4) To be performed only if the IOP is not stable at the Week 12 visit or if the ophthalmologist judges that it is necessary.
- (5) Azopt® must be stopped for 2 weeks before the Randomisation Visit.
- (6) Slit lamp examination: Score of each ocular sign (blepharitis, eyelid oedema, iris pigmentation modification, abnormal eyelashes aspect, folliculo-papillary conjunctivitis or other ocular abnormality) will be recorded in each eye using 0-3 scale.
- (7) Urinary test to be done for childbearing potential women.
- (8) Run-in treatment (Azopt®) will be instilled by the patient one drop in each eye twice a day (morning and evening) for 5 weeks.
- (9) One drop of IP (T4032 or Lumigan®) will be instilled by the patient in each eye once daily at 20:00 (\pm 1 hour) for 12 weeks.
- (10) Efficacy and ocular tolerance will be assessed by the investigator and the patient as very satisfactory, satisfactory, not very satisfactory, or unsatisfactory.
- (11) In case of AE, all treatments of the follow-up period will be collected.

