7.10 Ocular and systemic adverse events

All AEs reported during the study will be coded with MedDRA version the most recent possible at the database lock.

Ocular and systemic AEs will be analysed separately on the basis of the localisation as recorded by the investigator in the CRF.

Summary tables will be produced for treatment-emergent AEs (TEAEs).

TEAEs for Azopt® are AEs that occurred the same day or after the first Azopt® instillation and until the day of the first IMP (LT4032 or Lumigan®).

TEAEs for LT4032 or Lumigan® are AEs that occurred the same day or after the first IMP (LT4032 or Lumigan®) instillation and before or the day of the maximal date between last IMP instillation and Visit 4 (Week 12).

AEs that occurred the day of the first Azopt® instillation will be reviewed during a blind review meeting to decide if they have to be considered as a TEAE for Azopt® or not. AEs that occurred the day of the first IMP instillation will be reviewed during a blind review meeting to decide if they have to be considered as a TEAE for LT4032 or Lumigan® or a TEAE for Azopt®.

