Population: m-ITT set

Page X / N

Table 2.5 – Systemic surgical history by SOC and PT – m-ITT set
Same as Table 2.3

Name of SAS program: B:\THEA\LT4032-301\Analyse\Pgm\nom_du_programme.sas
Date and time program was run: JJMMYY HH:MM

Study: LT4032-301
Population: m-ITT set

Page X / N

Table 2.6 – Previous ocular treatments by WHO-Drug ATC2 and ATC4 – m-ITT set

	T4032 (N=XX)	Lumigan (N=XX)	Total (N=XX)
Any previous ocular treatment	xx (xx.x%)	xx (xx.x%)	xx (xx.x%)
ATC class 2_1	xx (xx.x%)	xx (xx.x%)	xx (xx.x%)
ATC class 4_1_1	xx (xx.x%)	xx (xx.x%)	xx (xx.x%)
ATC class 4_1_2	xx (xx.x%)	xx (xx.x%)	xx (xx.x%)
...			
ATC class 2_2	xx (xx.x%)	xx (xx.x%)	xx (xx.x%)
ATC class 4_2_1	xx (xx.x%)	xx (xx.x%)	xx (xx.x%)
ATC class 4_2_2	xx (xx.x%)	xx (xx.x%)	xx (xx.x%)
...			

Name of SAS program: B:\THEA\LT4032-301\Analyse\Pgm\nom_du_programme.sas
Date and time program was run: JJMMYY YYYY HH:MM

Study: LT4032-301
Population: m-ITT set

Page X / N

Table 2.7 – Concomitant ocular treatments by WHO-Drug ATC2 and ATC4 – m-ITT set

Same as Table 2.6

Name of SAS program: B:\THEA\LT4032-301\Analyse\Pgm\nom_du_programme.sas
Date and time program was run: JJMMYY YYYY HH:MM

Study: LT4032-301
Population: m-ITT set

Page X / N

Table 2.8 – Previous non-ocular treatments by WHO-Drug ATC2 and ATC4 – m-ITT set

Same as Table 2.6

Name of SAS program: B:\THEA\LT4032-301\Analyse\Pgm\nom_du_programme.sas
Date and time program was run: JJMMYY YYYY HH:MM

Study: LT4032-301
Population: m-ITT set

Page X / N

Table 2.9 – Concomitant non-ocular treatments by WHO-Drug ATC2 and ATC4 – m-ITT set

Same as Table 2.6

Name of SAS program: B:\THEA\LT4032-301\Analyse\Pgm\nom_du_programme.sas
Date and time program was run: JJMMYY YYYY HH:MM

Study: LT4032-301
Population: m-ITT set

Page X / N

Table 2.10 – History of glaucoma or ocular hypertension – Diagnosis – Worse eye – m-ITT set

	T4032 (N=XX)	Lumigan (N=XX)	Total (N=XX)
Diagnosis			
n	xx	xx	xx
Ocular hypertension	xx (xx.x%)	xx (xx.x%)	xx (xx.x%)
95% CI (Ocular hypertension)	[xx.x%;xx.x%]	[xx.x%;xx.x%]	[xx.x%;xx.x%]
Primary open angle glaucoma	xx (xx.x%)	xx (xx.x%)	xx (xx.x%)
95% CI (Primary open angle glaucoma)	[xx.x%;xx.x%]	[xx.x%;xx.x%]	[xx.x%;xx.x%]
Secondary open angle glaucoma: Exfoliation Glaucoma	xx (xx.x%)	xx (xx.x%)	xx (xx.x%)
95% CI (Secondary open angle glaucoma: Exfoliation Glaucoma)	[xx.x%;xx.x%]	[xx.x%;xx.x%]	[xx.x%;xx.x%]
Secondary open angle glaucoma: Pigmentary Glaucoma	xx (xx.x%)	xx (xx.x%)	xx (xx.x%)

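### SAP 5.2 gives concomitant treatment a start date but no end date, so recorded drugs begun after study treatment are tabulated as concomitant by arm

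*SAP*

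**What the plan says.** SAP 5.2 recognises two classes of treatment, previous and concomitant: "All previous and concomitant ocular and non-ocular treatments will be coded using the World Health Organisation-Drug Dictionary". The first limb of the concomitant definition reads "A concomitant treatment will be defined as a treatment i) started after (or the same day as) the first instillation" of study drug. The second reads "ii) started prior to and continued after the first instillation of the T4032/ Lumigan". Unresolved dates go the same way: "If the classification is not possible due to partial start/end date(s) of treatment, the treatment will be considered as concomitant". Results are summarised at ATC levels 2 and 4 "of the WHO-DD dictionary by treatment group and overall", for example in "Table 2.7 – Concomitant ocular treatments by WHO-Drug ATC2 and ATC4 – m-ITT set". The same table is planned for the Safety set (2.55), the ITT set (2.124, if that set differs from the Safety set) and the PP set (2.176). The non-ocular counterparts are 2.9, 2.57, 2.126 and 2.178.

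Footnote (11) to the flow chart in SAP 1.2.2, repeated under Table 2 of the protocol, says: "In case of AE, all treatments of the follow-up period will be collected".

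For AEs, SAP 7.10 does close the period. An event is treatment-emergent for T4032 or Lumigan if it occurs on or after the first instillation and "before or the day of the maximal date between last IMP instillation and Visit 4 (Week 12"). SAP 7.10.3 puts later events in a separate post-treatment listing.

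**The concern.** A table of concomitant treatment by arm tells the reader what patients used alongside study drug while IOP and tolerance were being measured. With no end date, it also counts drugs begun after study drug had stopped, and nothing in the table separates the two.

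Follow-up treatments are also not collected from everyone on the same terms. Their collection is tied to an AE, and the trial compares a preserved with an unpreserved product, so AE rates may differ between arms. If they do, the arm with more AEs has more follow-up drugs recorded, and those drugs appear as heavier concomitant use. A reader could take this for a difference in on-treatment medication.

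SAP 8 records that the AE emergence period was reviewed partly because a follow-up visit takes place. The treatment definition faces the same follow-up period and has no matching bound, which suggests an oversight rather than a choice.

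**Working it through.** No figure in the plan bears on this point, so the check is a reading of the rule plus date arithmetic.

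1. **Is there an end date?** The first limb compares a start date with the first instillation only. The second limb covers drugs already in use that continue past the first instillation. These overlap study treatment by construction, so they need no upper bound. The gap lies in the first limb. No section on visits, missing data, derived data or AEs supplies a bound for treatments.

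2. **Are there records for the gap to catch?** Yes. Footnote (11) provides for follow-up treatments to be collected in case of AE. In addition, SAP 4.2 places the premature discontinuation visit after the patient stops study drug, so a drug begun in between can be recorded there.

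3. **Same day, two rules.** Take a completer with Visit 4 on Day 84 who has an AE, and starts a drug for it, between then and the Day 112 call. Under SAP 7.10 and 7.10.3 the AE is post-treatment. Under SAP 5.2 the drug is concomitant. If a patient without an AE starts the same drug, footnote (11) does not call for it to be recorded.

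4. **Calendar time left open** (Visit 4 at Day 84 ± 7, call at Day 112 ± 7, counting days after Day 1):
   - Nominal: 112 − 84 = 28 days; 28 / (112 − 1) = 25%.
   - Shortest: 105 − 91 = 14 days; 14 / (105 − 1) = 13%.
   - Longest: 119 − 77 = 42 days; 42 / (119 − 1) = 36%.
   - A patient who stops at Day 42, if records run to Day 112: 70 / 111 = 63%.

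   These are shares of time, not of patients or table entries.

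5. **How an arm difference could arise** (assumed rates; the documents give none). Let a be the proportion of an arm with AE-triggered collection. Let q be the proportion of those patients who start a drug of a given class in follow-up and are not already counted for it. With q equal in both arms, the spurious gap is q × (difference in a).
   - q = 1, the upper limit: 5% versus 10% gives 5 points; 10% versus 20% gives 10 points.
   - q = 0.5: the same rates give 2.5 and 5 points.
   - Equal a: no gap.

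6. **Which cut-off?** Dosing is at 20:00 and Visit 4 IOP is read at 08:00, 10:00 and 16:00, so the last drop before those readings normally falls on the previous evening. A cut-off at the last instillation would label as post-treatment a drug begun before the Visit 4 readings. The same would happen to a drug begun between stopping and a premature discontinuation visit, whose IOP SAP 4.2 allows into the analysis after blind review. Either drug could affect analysed IOP. The later of last instillation and final visit keeps both. Its one weakness is a drug begun on the final-visit day after the readings, which the date alone cannot separate.

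**The case against.** The strongest reply is that these tables carry little weight. They are descriptive and feed no model, analysis set or non-inferiority decision. Prohibited treatment is handled elsewhere: deviations are classed at a blind review (SAP 2.4), tabulated by arm and listed by patient (SAP 5.1, Table 1.28, Listing 1.4), and all e-CRF data are listed by patient (SAP 3). All of this stands, and it limits the importance of the point. It does not make the definition right.

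Three stronger readings are tempting, and the documents do not support them.

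- **Every patient who returns to glaucoma therapy will add a false concomitant entry.** Neither document names replacement therapy or says that a drug started at or after Visit 4 is recorded for all patients. If follow-up treatments are collected in case of AE, a completer without an AE may have nothing on file. Replacement therapy enters only if recorded, which depends on the e-CRF.
- **A quarter of the data behind the tables is off-treatment.** The 25% is calendar time. For patients without an AE, most of it may contribute no entry.
- **On-treatment use of a prohibited drug cannot be detected.** It cannot be isolated in these tables, but the deviation review and the listings capture it.

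The scope of footnote (11) is also uncertain. Collection only from patients with an AE is its natural reading, but the word only is absent, and the flow-chart text available does not show which cell carries the footnote.

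**Conclusion.** The concern holds as a defect of definition. As written, SAP 5.2 classes any recorded drug started after study treatment as concomitant and tabulates it by arm. Where such records exist because of an AE, a difference in AE rates can produce an apparent difference in concomitant use. The size cannot be computed: the documents give no AE rates, no counts of follow-up drugs and no e-CRF detail, and the gaps in the working rest on assumed rates. The conclusion assumes that footnote (11) operates as worded and that the collected treatments are stored with the other treatment records. The effect is confined to descriptive tables, and the primary non-inferiority analysis is not affected. The change is worth making before database lock because it is cheap and brings treatments into line with the SAP's own AE rule.

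**What to change.** In SAP 5.2:

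- End the first limb at the later of the last T4032/Lumigan instillation and Visit 4, or the premature discontinuation visit where that replaces it. This matches SAP 7.10.
- Within the concomitant tables, show separately the treatments started on the day of that final visit after the last instillation.
- Add a post-treatment class for later starts and list it, with a note that follow-up treatments were collected in case of AE.
- Keep the present default to concomitant where partial dates leave the class open.

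The cost is a sentence or two of text, a date condition in the programs and one extra listing. The last-instillation date is already used in SAP 4.3.7, and the visit dates are used in the compliance calculations in SAP 4.3.9, so no new data are needed.

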5.3 Treatment exposure and compliance

The following data on the use of Azopt® will be summarised overall for the Azopt® Safety set and by treatment group for the m-ITT set:

- Duration of Azopt® (days)
- Frequency distribution of patients with any absence or modification of Azopt® instillation (Yes/No) from the first to the last instillation

The following data on the use of Azopt® will be summarised by treatment group for the m-ITT set:

- Compliance (%) for each eye from the first to the last instillation, as continuous variable and in categories (<80%, ≥80% and ≤120%, >120%)

Details of data relative to Azopt® instillation and modification of Azopt® instillation will be provided in individual data listing.

The following data on the use of the IMP T4032 or Lumigan® will be summarised overall and by treatment group for the Safety and m-ITT sets and it will also be summarised by possible impact of COVID-19 pandemic classes:

- Duration of treatment (days)
- Frequency distribution of patients with any absence or modification of instillation (Yes/No) from the first to the last instillation, between Day 1 and Week 6, Week 6 and Week 12, Day 1 and Week 12
- Frequency distribution of patients with any instillation time modifications (Yes/No) from the first to the last instillation, Day 1 and Week 6, Week 6 and Week 12, Day 1 and Week 12
- Compliance (%) for the worse and contralateral eye from the first to the last instillation, from Day 1 and Week 6, Week 6 and Week 12, Day 1 and Week 12, as continuous variable and in categories (<80%, ≥80% and ≤120%, >120%)

Details of data relative to IMP instillation, absence of instillations and instillation time modifications will be provided in individual data listings.

6 EFFICACY ANALYSIS

The primary efficacy endpoint will be primarily analysed on the m-ITT set. Sensitivity analyses will be performed on the ITT and PP sets. Secondary efficacy endpoints will be analysed on the m-ITT set and on PP set.

For efficacy variables, descriptions will be given by treatment group at each assessment time. Change from baseline will also be presented.

Of note, for analyses on change from baseline in IOP at 10:00 (respectively at 16:00) in the worse eye and in the contralateral eye, the baseline IOP is the IOP recorded at 10:00 (respectively at 16:00) at Day 1, before the first instillation.

